11.3.1. Change in FEV₁ from Baseline through End of Study

Forced Expiratory Volume in 1 second (FEV₁) (L) change from baseline and % Predicted FEV₁ change from baseline will be summarized by visit using summary statistics for continuous variables.

Percent predicted FEV₁ (%) will be calculated by implementing the Global Lungs Initiative 2012 regression equations. The predicted value of FEV₁ is a function of sex, age, height, and ethnicity and is of this form:

$$M = \exp(a_0 + a_1 \cdot \ln(\text{Height}) + a_2 \cdot \ln(\text{Age}) + a_3 \cdot \text{black} + a_4 \cdot \text{NEAsia} + a_5 \cdot \text{SEAsia} + a_6 \cdot \text{Other} + \text{Mspline})$$

M = predicted value

Exp = exponential function

ln() = natural log transformation

black = 1 if a subject is Black or African American, otherwise = 0

NEAsia = 1 if a subject is from North East Asia, otherwise = 0

SEAsia = 1 if a subject is from South East Asia, otherwise = 0

Other = 1 if subject is 'other ethnic group' or mixed ethnicity (i.e., subject is not indicated to be from North East Asia, South East Asia, or African American from eCRF page 'Demographics'), otherwise = 0

coefficients a0... a6 depend on the measurement and gender

Mspline = age and sex varying coefficients provided by Qanjer PH, Stanojevic S, Cole TF, et al.

The coefficients and Mspline values used for predicted FEV₁ calculations are provided in [Appendix 15.3](#).

Finally, % predicted = (measured/M) * 100.

This document is confidential.

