8.2. Demographic and Baseline Characteristics

Descriptive summaries of demographic and baseline characteristics will be presented by each cohort and overall, for the Safety Population. The demographic data includes: age at screening (in years), sex at birth, race, ethnicity/geographic origin (North East Asian or South East Asian), height (cm), weight (kg), BMI (kg/m²), and for females, childbearing potential. Baseline disease characteristics include forced expiratory volume [FEV₁ (L)], forced expiratory volume (FEV₁) % Predicted, forced vital capacity [FVC (L)], forced expiratory flow between 25 and 75% of the FVC [FEF₂₅₋₇₅ (L)], Quality of Life Bronchiectasis (QOL-B) scale scores, Leicester Cough Questionnaire (LCQ) score, and Saint George's Respiratory Questionnaire (SGRQ) score.

Height (in m) = height (in cm) / 100

BMI (kg/m²) = Weight(kg)/[Height(m)²]

Demographics and Baseline characteristics will be listed by subject for the Safety Population.

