11.3. Spirometry

Spirometry assessments FEV₁, FVC, and FEF₂₅₋₇₅ will be collected locally at the clinical study site. Actual liter values will be recorded. Details regarding spirometry procedures and standards will be included in the Study Manual. Spirometry will be assessed according to the Schedule of Assessments in Table 1 of the Protocol Appendix A and Timing of Sample Collection and Procedures for the Treatment Period in Table 2 of the Protocol Appendix A. Spirometry will be collected prior to sputum induction on non-Treatment Period Visits.

Observed values and mean changes from baseline will be presented for each spirometry parameter using descriptive statistics (i.e., n, mean, standard deviation, median, minimum, and maximum) by treatment group and visit, using the Safety population. If multiple measurements are to be performed at each time

This document is confidential.

point, the highest value will be used for analysis.

A by-subject listing will be provided, including each spirometry parameter, and will be sorted by subject and visit.

A by-subject line plot will be presented by spirometry parameter and cohort. Each cohort will be on a new plot, with all subjects of the same cohort on the same plot. Any unscheduled results will also be part of this plot.

The number and percentage of subjects with PCS values will be summarized by visit/timepoint and for any time post-baseline. Potentially clinically significant values will be identified for FEV₁ (forced expiratory volume) as outlined below.

Table 13.6.1 Potentially Clinically Significant Values for Forced Expiratory Volume Decrease

Parameter	Units	Criteria for PCS Values (Observed values)	
		High	Low
Forced Expiratory Volume	%	NA	70 – 99 60 – <70 50 – <60 <50

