16.3. Global Lung Function Initiative (GLI) Regression Coefficients

The linear coefficients used in conjunction with the Mspline values include the following:

Males:

Intercept	a0	-10.3420
Height	a1	2.2196
Age	a2	0.0574
Afr. Am.	a3	-0.1589
N East Asia	a4	-0.0351
S East Asia	a5	-0.0881
Other/mixed	a6	-0.0708
		Mspline

Females:

Intercept	a0	-9.6987
Height	a1	2.1211
Age	a2	-0.0270
Afr. Am.	a3	-0.1484
N East Asia	a4	-0.0149
S East Asia	a5	-0.1208
Other/mixed	a6	-0.0708
		Mspline

Mspline lookup values from Qanjer PH, Stanojeciv S, Cole TF, et al.:

Age	Mspline - Female	Mspline - Male
3	-0.2311	-0.1133
3.25	-0.2170	-0.1073
3.5	-0.2040	-0.1011
3.75	-0.1922	-0.0951
4	-0.1817	-0.0893
4.25	-0.1727	-0.0841
4.5	-0.1651	-0.0799
4.75	-0.1592	-0.0769
5	-0.1548	-0.0752
5.25	-0.1518	-0.0750
5.5	-0.1494	-0.0758
5.75	-0.1474	-0.0771
6	-0.1452	-0.0787
6.25	-0.1426	-0.0803
6.5	-0.1393	-0.0816

This document is confidential.

Statistical Analysis Plan for Interventional Studies
Sponsor: Armata Pharmaceuticals, Inc.; Protocol No.: AP-PA02-201

6.75	-0.1354	-0.0823
7	-0.1310	-0.0822
7.25	-0.1264	-0.0815
7.5	-0.1217	-0.0804
7.75	-0.1171	-0.0792
8	-0.1125	-0.0778
8.25	-0.1076	-0.0763
8.5	-0.1022	-0.0745
8.75	-0.0963	-0.0721
9	-0.0897	-0.0691
9.25	-0.0825	-0.0658
9.5	-0.0747	-0.0622
9.75	-0.0663	-0.0586
10	-0.0573	-0.0549
10.25	-0.0479	-0.0513
10.5	-0.0380	-0.0476
10.75	-0.0278	-0.0437
11	-0.0172	-0.0395
11.25	-0.0063	-0.0350
11.5	0.0048	-0.0299
11.75	0.0161	-0.0241
12	0.0274	-0.0176
12.25	0.0386	-0.0101
12.5	0.0496	-0.0019
12.75	0.0604	0.0071
13	0.0709	0.0169
13.25	0.0810	0.0274
13.5	0.0907	0.0384
13.75	0.0999	0.0497
14	0.1086	0.0612
14.25	0.1168	0.0728
14.5	0.1244	0.0844
14.75	0.1315	0.0958
15	0.1379	0.1068
15.25	0.1438	0.1175
15.5	0.1492	0.1276
15.75	0.1540	0.1371
16	0.1583	0.1460
16.25	0.1621	0.1542
16.5	0.1655	0.1616

This document is confidential.

16.75	0.1684	0.1684
17	0.1711	0.1744
17.25	0.1733	0.1798
17.5	0.1753	0.1845
17.75	0.1770	0.1887
18	0.1785	0.1924
18.25	0.1797	0.1956
18.5	0.1808	0.1984
18.75	0.1816	0.2008
19	0.1823	0.2029
19.25	0.1829	0.2046
19.5	0.1833	0.2060
19.75	0.1837	0.2072
20	0.1839	0.2081
20.25	0.1841	0.2087
20.5	0.1842	0.2090
20.75	0.1842	0.2092
21	0.1841	0.2091
21.25	0.1840	0.2089
21.5	0.1838	0.2084
21.75	0.1835	0.2079
22	0.1832	0.2071
22.25	0.1828	0.2063
22.5	0.1823	0.2053
22.75	0.1818	0.2042
23	0.1812	0.2030
23.25	0.1806	0.2016
23.5	0.1799	0.2002
23.75	0.1792	0.1987
24	0.1785	0.1970
24.25	0.1777	0.1954
24.5	0.1769	0.1936
24.75	0.1761	0.1918

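### SAP 11.3.1 codes every subject outside three named groups as GLI Other, so no reference group remains; coded literally, % predicted FEV₁ is 7.3% too high (relative) for reference subjects, who by elimination are White

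*SAP*

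**What the plan says.** SAP 11.3.1 derives predicted FEV₁ as the exponential of an intercept, log height, log age, four ethnicity terms and an age- and sex-specific spline value. % predicted is measured FEV₁ divided by that prediction, times 100. Three of the indicators are plain. The first is "black = 1 if a subject is Black or African American, otherwise = 0"; the next two work in the same way for people of North East Asian and of South East Asian origin.

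The fourth begins narrowly: "Other = 1 if subject is 'other ethnic group' or mixed ethnicity". A bracketed i.e. clause in the same sentence then spells this out as the case where the "subject is not indicated to be from North East Asia, South East Asia, or African American from eCRF page" for demographics.

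SAP 16.3 lists the coefficients by sex. The rows are intercept, height, age, African American, North East Asia, South East Asia and Other/mixed. There is no row for White subjects, and neither document names a reference group. SAP 8.2 lists "race, ethnicity/geographic origin (North East Asian or South East Asian") among the demographic data, so race is held separately from Asian origin.

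**The concern.** With an intercept and four indicators, the intercept alone must describe some fifth group. The bracketed clause removes it: a subject without one of the three named flags is automatically Other. The sentence therefore gives two different definitions, a specific category first and then everyone who is left. The second is the one tied to a data source, the eCRF demographics page, so it reads as the programming rule.

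Two planned outputs would be wrong: the baseline characteristic % predicted FEV₁ (SAP 8.2), where disease would look milder than it is, and the by-visit change in % predicted FEV₁ (SAP 11.3.1). A third, the bands in the SAP 11.3 table titled "Potentially Clinically Significant Values for Forced Expiratory Volume Decrease", is exposed only if its percentage means % predicted, which the table does not say.

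**Working it through.** The plan gives no worked predicted value, so there is no figure of its own to reproduce. The check evaluates the SAP's equation twice for the same subject, with Other = 0 and with Other = 1.

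**Can anyone be in the reference group?**

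| Subject flagged as | black | NEAsia | SEAsia | Other, literal clause | Other, other/mixed only |
|---|---|---|---|---|---|
| Black or African American | 1 | 0 | 0 | 0 | 0 |
| North East Asian | 0 | 1 | 0 | 0 | 0 |
| South East Asian | 0 | 0 | 1 | 0 | 0 |
| Other or mixed | 0 | 0 | 0 | 1 | 1 |
| None of these (by elimination, White) | 0 | 0 | 0 | **1** | **0** |

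The last row is the only one that differs. Under the literal clause no row has four zeros.

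**Size of the error.** The Other/mixed coefficient is a6 = -0.0708 for men and for women (SAP 16.3). All other terms cancel in the ratio, so it is the same at every age and height:

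- predicted, Other = 1 over Other = 0: exp(-0.0708) = 0.9316, i.e. 6.8% too low
- % predicted, Other = 1 over Other = 0: exp(0.0708) = 1.0734, i.e. 7.3% too high

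| Reference-coded % predicted | Reported if coded Other | Difference (points) |
|---|---|---|
| 35 | 37.6 | +2.6 |
| 50 | 53.7 | +3.7 |
| 60 | 64.4 | +4.4 |
| 70 | 75.1 | +5.1 |

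**Two worked subjects.** Coefficients and age-65 spline values are from SAP 16.3; age, height and FEV₁ are assumed for illustration.

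Woman, 65 years, 162 cm, FEV₁ 1.50 L:
- Other = 0: exp(-9.6987 + 2.1211 × ln 162 - 0.0270 × ln 65 - 0.1308) = 2.338 L, so 64.2% predicted
- Other = 1: 2.338 × 0.9316 = 2.178 L, so 68.9% predicted (+4.7 points)
- a 0.1 L change is 4.28 points with Other = 0 and 4.59 with Other = 1

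Man, 65 years, 175 cm, FEV₁ 1.80 L:
- Other = 0: exp(-10.3420 + 2.2196 × ln 175 + 0.0574 × ln 65 - 0.1727) = 3.283 L, so 54.8% predicted
- Other = 1: 3.283 × 0.9316 = 3.058 L, so 58.9% predicted (+4.0 points from unrounded values)
- a 0.1 L change is 3.05 points with Other = 0 and 3.27 with Other = 1

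Relative change is unaffected because the factor cancels: 1.50 to 1.40 L is -6.7% under either coding.

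**FEV₁ bands, conditionally.** If the percentage in the SAP 11.3 table is % predicted, a correct value from 70 / 1.0734 = 65.2% up to just under 70% would be reported at 70% or more, and would move from the 60 to <70 band to the 70 to 99 band.

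**The case against.** The strongest reply is that this is loose wording and that no coefficient or formula is wrong. The opening words of the definition, the Other/mixed label in SAP 16.3 and the SAP's reliance on the published GLI 2012 equations all point to the narrow category, and a programmer who followed them would code it correctly. That is fair, and it is why the numerical error is conditional on literal coding. It does not remove the defect: the clause that names the data source is the broad one, nothing elsewhere corrects it, and an independent validation programmer working from the same text could reproduce the same mistake.

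It can also be said that White is an inference. The eCRF page and its race categories are not in the documents, and any other category without an indicator would be caught in the same way. This stands as a caveat. The empty reference group does not depend on it, but the label put on the affected subjects does. The racial mix is unknown too, so the effect on a table mean cannot be sized.

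Finally, the consequences are modest. The multiplier is fixed for each subject and does not depend on treatment. For a 0.1 L change the distortion is 0.2 to 0.3 points in the worked examples. Spirometry change is an exploratory, descriptive endpoint, and litres are summarised alongside. All of this is correct. It limits the importance of the point but does not make the reported % predicted values right.

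**Conclusion.** The concern holds. The bracketed clause in SAP 11.3.1 leaves the equation without a reference group. Coded literally, it overstates % predicted FEV₁ by 7.3% in relative terms for every subject who belongs in that group, which is about 3 to 5 points for values between 35% and 70%, and it stretches absolute changes by the same factor. This rests on two assumptions: that the clause is followed as written, and that the unnamed reference group is White.

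The primary endpoint, FEV₁ in litres and relative within-subject change are not affected. Screening eligibility also uses a GLI % predicted value (Protocol 4.1 and 8.8), but nothing in the documents shows that it uses this coding. The point should be fixed before the derivation is programmed or finalised; it does not threaten the trial's main conclusion.

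**What to change.** In SAP 11.3.1, delete or correct the bracketed clause so that Other is 1 only for subjects recorded as other or mixed ethnicity. Add a sentence stating that White subjects are the reference group, with black, NEAsia, SEAsia and Other all 0. Before finalising, confirm that the race categories on the eCRF demographics page separate White from other or mixed. SAP 8.2 shows that race is collected, so no new data should be needed. The cost is one line of SAP text and one line of the derivation program.

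Two optional additions: where sites recorded % predicted FEV₁ at Screening, compare it with the derived value as a check; and state what the percentage in the SAP 11.3 FEV₁ table refers to. The main correction does not depend on either.

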11.4. Clinical Laboratory Evaluations

Clinical laboratory measurements (chemistry, hematology, coagulation, and urinalysis) will be obtained at Screening, Baseline, and subsequent study visits according the Schedule of Assessments in Table 1 of the Protocol Appendix A, and will be summarized by treatment group in the following ways:

- Descriptive statistics of actual results and changes from baseline (number of subjects, mean, standard deviation, median, minimum, and maximum) for the continuous data and frequencies and percentages for the categorical data, for each assessment visit.
- Potentially clinically significant lab abnormalities for hematology, chemistry, and coagulation will be summarized by assessment visit.
- By-subject line plots will be presented by lab parameter to allow for significant out of range values to be further defined.

By-subject safety laboratory listings will be generated incorporating information and assessment results obtained from the designated laboratory which provided normal range and reported out of range results. All laboratory results in SI units will be presented in data listings. Tests will be listed in alphabetical order within their respective panels (standard safety chemistry, hematology, coagulation, and urinalysis).

Potentially clinically significant chemistry and hematology laboratory results will be summarized using severity grades according to NCI CTCAE (version 5.0 or higher) where applicable. The worst post-baseline severity grade will be summarized and is defined as the most severe toxicity grade of the specific parameter assessed during the study at a scheduled or unscheduled visit. If a severity grade scale is missing for a laboratory parameter, the normal ranges of the clinical laboratory will be used.

11.4.1. Chemistry

Serum chemistries will include alanine aminotransferase, albumin, alkaline phosphatase, amylase, aspartate aminotransferase, bicarbonate, blood urea nitrogen, calcium, chloride, creatine kinase, creatinine, creatinine clearance, estimated glomerular filtration rate, gamma-glutamyl transferase, glucose, inorganic phosphorus, lactate dehydrogenase, lipase, potassium, sodium, total bilirubin, total protein, and uric acid. Creatinine clearance is to be calculated using the Cockcroft-Gault equation adjusted for actual body weight.

11.4.2. Hematology

Hematology will include a complete blood count (CBC), which includes hematocrit, hemoglobin, platelet count, red blood cell count, and white blood cell count and differential.

11.4.3. Coagulation

Coagulation testing will include international normalized ratio.

11.4.4. Urinalysis

Urinalysis will be performed at the local laboratory at time points designated in the Timing of Sample Collection and Procedures for the Treatment Period in Table 2 of the Protocol Appendix A. Urinalysis will be performed by visual inspection and dipstick, and will include bilirubin, blood, glucose, ketones, leukocyte esterase, microscopy, nitrite, pH, protein, specific gravity, and urobilinogen. In addition, microscopy will be performed only as needed based on abnormal dipstick test results.

This document is confidential.

11.5. Vital Signs

Vital sign measurements will consist of blood pressure (systolic and diastolic), oxygen saturation, heart rate, respiratory rate, and body temperature. Descriptive summaries (number of subjects, mean, standard deviation, median, minimum, and maximum) of actual values and changes from baseline will be presented for each visit and time point. These summaries will be presented for the safety population and by treatment group. Vital signs will be performed at all study visits at prespecified time points per the Timing of Sample Collection and Procedures for the Treatment Period in Table 2 of the Protocol Appendix A.

Temperature will be summarized in Celsius (C) units. Fahrenheit (F) will be converted to Celsius using the following conversion:

$$\text{Temperature (in } ^\circ\text{C)} = 5/9 \text{ (Temperature [in } ^\circ\text{F]} - 32)$$

Potentially clinically significant (PCS) vital sign abnormalities will be categorized based on Table 13.3.1 and summarized by treatment group and assessment visit.

Table 13.3.1 Potentially Clinically Significant Values for Vital Signs

Vital Sign Parameter	Units	Criteria for PCS Values (Observed values)		Criteria for PCS values (Change from Baseline values)	
		High	Low	Increase	Decrease
Heart rate (sitting)	Beats/min	>120	<40	NA	NA
Systolic Blood Pressure (sitting)	mmHg	>180	<90	≥30	≥30
Diastolic Blood pressure (sitting)	mmHg	>110	<50	≥20	≥20
Oxygen Saturation (sitting)	%	NA	<92	≥5	≥5

A by-subject line plot will be provided by treatment group. Vital sign data will be listed chronologically by subject and visit for each vital sign parameter.

11.6. Twelve-Lead Electrocardiograms

A 12-lead ECG will be performed locally at the site according to the Schedule of Assessments in Table 1 of the Protocol Appendix A and Timing of Sample Collection and Procedures for the Treatment Period in Table 2 of the Protocol Appendix A for all subjects. The Fridericia formula for calculating QTc will be used (i.e., QTcF).

A shift table of the Investigator's assessment of ECG results at each visit compared with baseline values will be presented by treatment group using the following categories: normal; abnormal (not clinically significant); abnormal (clinically significant). The number and percentage of subjects in each cross-classification group of the shift table will be presented by treatment group. Subjects with a missing value at baseline or post baseline will not be included in the denominator for percentage calculation.

This document is confidential.

A by-subject listing will be provided, including each ECG parameter: ventricular heart rate (beats per minute [bpm]), PR interval [msec], RR interval [msec], QRS Duration [msec], QT interval [msec], QTcB interval [msec], QTcF interval [msec], and Investigator's interpretation. Potentially clinically significant QTcF values will be flagged in the listing.

The number and percentage of subjects with PCS and potentially clinically significant change (PCSC) values will be summarized by visit/timepoint and for any time post-baseline. Potentially clinically significant values will be identified for ECG parameters as outlined below.

Table 13.4.1 Potentially Clinically Significant Values for QT and QTcF

ECG Parameter	Units	Criteria for PCS Values (Observed values)		Criteria for PCS values (Change from Baseline values)	
		High	Low	Increase	Decrease
QT, QTcF	msec	>450 but <=480 >480 but <=500 >500	NA	>=30 to 60 >60	NA

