1.3.2.2 Potential Risks

All therapies have the potential to cause adverse experiences. The risks associated with blood sampling for safety or pharmacokinetic purposes are limited and the volume of blood needed is well below the acceptable limits for adults. Study intervention will be provided in addition to, not in replacement of, standard of care supportive and symptomatic therapy.

The risks of nebulized phage therapy may include bronchial irritation and/or immune response to phages. As such, subjects will be monitored closely on Day 1 of dosing under clinical supervision with regularly scheduled vital sign, spirometry, and AE assessments. In addition, sentinel dosing, individual subject stopping criteria, and study stopping criteria are included as part of the study conduct.

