8.12 Twelve-Lead Electrocardiograms

Twelve-lead ECGs will be performed according to the Schedule of Assessments and Timing of Sample Collection and Procedures for the Treatment Period ([Appendix A](#)). The Fridericia formula for calculating QTc will be used.

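### SAP Tables 13.4.1 and 13.3.1 count heart-rate effects on uncorrected QT, and rises in oxygen saturation, as potentially clinically significant

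*SAP*

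**What the plan says.** **ECG.** SAP Section 11.6 contains "Table 13.4.1 Potentially Clinically Significant Values for QT and QTcF". Its single row is for QT and QTcF together. The limits for observed values, in ms, are ">450 but <=480 >480 but <=500 >500". The limits for change from baseline are an increase of 30 to 60 ms and an increase above 60 ms. Low values and decreases are NA.

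The Protocol, Section 8.12, states: "The Fridericia formula for calculating QTc will be used". SAP 11.6 repeats this. On the listing, SAP 11.6 says: "Potentially clinically significant QTcF values will be flagged in the listing". On the summary table it says: "The number and percentage of subjects with PCS and potentially clinically significant change (PCSC) values will be summarized by visit/timepoint", and also for any time after baseline. The listing rule therefore covers QTcF alone, while the table covers QT as well.

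**Oxygen saturation.** SAP Section 11.5 contains "Table 13.3.1 Potentially Clinically Significant Values for Vital Signs". The saturation row has NA for a high observed value and below 92% for a low one. Under change from baseline it has 5 or more in both the increase and the decrease columns. Values meeting the table's criteria are summarised by treatment group and visit.

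**The concern.** A limit on a heart-rate-corrected interval and a limit on an uncorrected interval do not mean the same thing, even when the number is the same. Uncorrected QT lengthens when the heart slows. With shared cut-points, a subject whose heart rate falls between baseline and a later ECG can enter the QT change category with no change in QTcF. The count is arithmetically correct for QT, but it reports heart rate under a label that suggests a repolarisation finding.

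The saturation row has a similar labelling problem. A rise is an improvement unless the plan says otherwise, and the plan sets no upper limit on the observed value. Yet a rise of 5 or more is tabulated as an abnormality.

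What is at stake is the readability of two safety tables in small arms, where a single count moves a percentage visibly. The primary endpoint is not touched.

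**Working it through.** There is no planned figure to reproduce. The check applies the correction that the documents name to the limits that they set.

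**Inputs from the documents:** the cut-points in Table 13.4.1; the Fridericia correction (Protocol 8.12, SAP 11.6); the saturation row of Table 13.3.1; 24 subjects per cohort at 2:1 (Protocol 9.2.4; SAP 4.3 says approximately 24).

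**Assumptions, not in the documents:** heart rates from 50 to 90 bpm and constant QTcF values of 400, 420 and 440 ms. These heart rates lie inside the SAP's own limits of below 40 and above 120 bpm.

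**Step 1: relation of QT to QTcF.** QTcF = QT / (60/HR)^(1/3), so QT = QTcF × (60/HR)^(1/3). The two are equal only when HR = 60.

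**Step 2: observed values.** At 50 bpm, (60/50)^(1/3) = 1.0627. A QT of 450 ms is then a QTcF of 450 / 1.0627 = 423.5 ms. A QT of 460 ms is a QTcF of about 433 ms. The second subject is counted in the lowest QT band although QTcF is below every limit.

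**Step 3: change from baseline with QTcF held constant.** Change in QT = QTcF × [(60/HR2)^(1/3) − (60/HR1)^(1/3)]. For 80 to 60 bpm the bracket is 1.0000 − 0.9086 = 0.0914.

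| Heart rate (bpm) | QTcF 400 | QTcF 420 | QTcF 440 | Counted as 30 to 60 ms? |
|---|---|---|---|---|
| 70 to 60 | +20.0 | +21.0 | +22.0 | No |
| 75 to 60 | +28.7 | +30.1 | +31.5 | At 420 and 440 |
| 80 to 60 | +36.6 | +38.4 | +40.2 | Yes |
| 90 to 70 | +30.5 | +32.1 | +33.6 | Yes |
| 90 to 60 | +50.6 | +53.1 | +55.6 | Yes |

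The true change in QTcF is 0 in every cell. A fall of 10 bpm does not reach the limit; falls of about 15 to 30 bpm can.

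**Step 4: table against listing.** The summary table counts QT and QTcF; the listing flags QTcF only. A subject counted on QT alone would therefore appear in the table with no flag in the listing to trace the count.

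**Step 5: saturation.** A change from 90% to 95% is +5 and meets the increase criterion. Since saturation cannot exceed 100%, this is possible for any baseline of 95% or below, and the eligibility criteria set no numerical floor for saturation. Across the two tables, this is the only cell that has a change limit in a direction where the observed-value limit is NA. In Table 13.4.1 the low and decrease cells are both NA. Blood pressure has limits in both directions of both kinds.

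**Step 6: weight of one count.** 24 × 2/3 = 16 and 24 × 1/3 = 8. One subject is 1/16 = 6.3% or 1/8 = 12.5%. SAP Section 6 excludes from most summaries the AP-PA02 subjects enrolled before the first DSMB meeting. The active denominator may therefore be below 16, and one count would then weigh more.

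**The case against.** Several points on the other side stand.

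- **QTcF is in the same row.** A reader might infer that long QTcF values at fast heart rates go unnoticed because QT is then short. The documents do not support that: QTcF is tested against the same limits and flagged in the listing. The only effect is extra counts on QT.
- **The artefact can be recognised.** The ECG listing shows heart rate, RR, QT and QTcF together. Scheduled ECGs after dosing are also few: one hour after the first dose on Day 1, then the end-of-study or early-termination visit.
- **The saturation columns are separate.** Gains mix with falls only if the output merges directions, and the table shell is not shown. The gain is still labelled potentially clinically significant, so this reduces the harm without removing it.
- **The reason for Fridericia is not given.** The Protocol names the formula only. The point rests on the shared cut-points and the mismatch with the listing rule, not on a stated intent.

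A reader might also infer, because temperature and respiratory rate have no row in Table 13.3.1, that fever and fast breathing cannot be counted. That goes too far. Clinically significant findings are reported as adverse events (Protocol 8.1), graded by CTCAE and tabulated. Both measures also have descriptive summaries at each visit and are listed, and SAP 11.5 provides by-subject plots of vital signs. Protocol 1.3.2.2 says "The risks of nebulized phage therapy may include bronchial irritation and/or immune response to phages", but it does not single out these two vital signs. Which vital signs receive a row is a choice that the sponsor may make.

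**Conclusion.** The point holds in a limited form. Table 13.4.1 applies one set of limits to a corrected and an uncorrected interval, against the SAP's own rule of flagging QTcF only. Table 13.3.1 labels an improvement in saturation as an abnormality, against its own NA for high values. Both follow from the text.

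The size is small. The QT example of about +37 to +40 ms depends on assumed heart rates and QTcF values. The documents do not show how often such falls in heart rate, or saturation gains of 5 or more, will occur. The weights of 6.3% and 12.5% assume the planned arm sizes. The saturation cell is read as percentage points. The effect is confined to descriptive safety tables; no QTcF signal is lost and no efficacy result changes.

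**What to change.** 1. In SAP Table 13.4.1, restrict the row and title to QTcF, which brings the table into line with the listing rule. Keep QT in the by-subject listing, where it already appears beside heart rate and QTcF.
2. In SAP Table 13.3.1, set the increase cell for oxygen saturation to NA, in line with its NA for a high observed value. If the sponsor wants to keep a count of rises, give the reason and report it outside the potentially clinically significant categories.

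The cost is two table edits and the matching output shells, made before unblinding. No new data and no change to the Protocol are needed.
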